By these means we will find pseudonymised NHS patients who have more than 3 long term conditions (LTC) which will be aligned with the capabilities of data collection of the smart technologies to be used during the study. Using this selection process, the research team aims to identify 700 pseudonymised NHS patients to be approached to participate in the study.

Each participant who consents to take part in the study will be issued with one or more of the smart technologies or sensor-based wearables which will not disturb their day to day activities. The allocation of these technologies is described in subsequent sections of this document. For a period of approximately six months we will record their vital signs and other readings in a secure cloud environment. Our data scientists and researchers will then be able to perform analyses and model development. This will conclude the first phase of the research (Phase 1).

In order to develop use cases, patient pathways and service recommendations, which may be largely based on those data collected, we will work with the CSU to ensure information governance permissions are in place to carry this out (Phase 2). We intend to make assessments of the likely qualitative and economic benefits of the predictive system based on the data collected. These will be tested through data quality evaluation, model selection, training data categorisation, learning algorithm(s), sensitivity and specificity analyses to help determine the confidence of the predictive systems (Ref: Longstaff 2010). The benefits can accrue in several parts of the "services". We will attempt to define the proportions in each.

2. Study Purpose

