3.4.3 Ongoing participant support

The participants will be supported for the trial by phone or email and speaking to one of our support staff at Optima. The support staff will also identify problems if there were a change in data flow from the devices from the participant, and seek to resolve them.

4. Smart Technologies

Each participant will be issued with one or more smart technology which will not disturb their day to day activities over the period of the study; during this period of time they will receive uninterrupted health care.

To gather meaningful information within the budget and time available, we need as large a sample size as possible which will also minimise the costs [of wearables]; it will facilitate the eventual solution economically scaling up to meet the rapidly growing and aging population. To meet the potential for scale, we will use a smart technology solution that is scalable and collects data from participants as passively and non-invasively as possible. This can involve looking at the camera on a tablet computer for thirty seconds or placing a finger over the camera on a smart phone for thirty seconds twice daily over the period of the programme. These smart technologies generate large volumes of raw data which will be pre-processed to identify discrete events or clinically meaningful and relevant measures.

The choice of the apps and wearables for an individual participant is carefully judged. We aim to achieve the "right app or wearable for the right patient" as accurately as we can. Since patients do not necessarily become ill with the same conditions they already have, apps may be chosen that do not relate to existing conditions. We will choose about a third of our participants from those who reside in a nursing care home and residential homes since they will tend to be sicker and more likely to have "an event" that may become predictable with the data collected. And also because some of our chosen apps can be used on more than one participant in a care home setting, this will provide coverage of participants with apps.

We believe the above approach to proven smart technologies will enable:

{i} Detection - of risk factors or undiagnosed conditions

{ii} **Protection** - from long term conditions by mitigation of risk through various interventions including social prescribing

{iii} Correction of conditions - many physical and chronic conditions are either reversible or the progress of the condition can be slowed

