5.1 Data Collection

5.1.1 Application of the i5 Diagnostic Stratification system

Helicon and its partner i5 Health will be applying the i5 Diagnostic Stratification system (i5 DST) – which uses algorithms based on Machine Learning, Neural Networks and Artificial Intelligence (AI) to analyse millions of clinical patterns from medical records to identify the most suitable cohort for this programme. More specifically, i5 DST is an algorithm-based Artificial Intelligence clinical evaluation tool that can identify undiagnosed patients with a high likelihood of having an undiagnosed Long Term Condition (LTC). It uses pseudonymised patient medical history and estimates the probability of the patient having or developing, an LTC. DST facilitates proactive patient management that delivers patient-centric care to reduce unscheduled admissions by targeting two groups of patients i.e. those with:

- High Probability of currently having an undiagnosed LTC
- Potential of developing an LTC in the near future

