The design of the input data set requires the size of the data set to be defined. A larger data set will require more time to train the machine learning algorithms. The balance between learning capability and learning time will be considered and set with outcome requirements. The methodologies for the clinical components are based on existing implementations of Neural Networks for preliminary diagnosis to support targeted screening in the NHS.

Developing of machine learning algorithms can be split broadly into five stages.

24

- a) Obtain data that is pseudonymised and consists of a representative cross-section of patients with and without the condition or an adverse event
- b) Reduce the number of feature parameters that are relevant using de-correlation methods such as Primary Component Analysis (PCA)
- c) Split the data for machine learning training, monitoring of overfitting and performance testing to facilitate evaluation of prediction quality and applicability
- d) Train various machine learning models and topologies to evaluate which combination works best for the required predictions
- e) At the end of the study, device data will be connected to primary and secondary care data to build full medical records of participating patients. Such longitudinal medical records facilitate the prediction of future events to deliver pro-active care.

Joining the Device Data with GP and Hospital data requires a consistent key across all three data sets. Depending on the data structures held at Arden and Gem (AGEM) CSU, the Trial IDs can be mapped to a clear either to clear or pseudonymised NHS number, with a preference for pseudonymised NHS numbers.

GP and Hospital data extraction will be performed by applying the list of participating patients as a filter. This filter will be the list of pseudonymised NHS number where possible. The resulting data structure will be a collection of clinical and non-clinical data sets that can be linked via a pseudonymised primary key, or NHS number, location and calendar date for air pollution or weather data. **See table E – above**

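### Section 5.2 calls the model data representative, but the cohort is deliberately risk-enriched: performance may not carry over, and care setting alone could look predictive

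*Protocol*

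**What the plan says.** Section 5.2 outlines machine-learning development in five broad stages. Stage (a) asks for pseudonymised data from a "representative cross-section of patients with and without the condition or an adverse event".

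The sections on selection describe something else:

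- Section 5.1.1: the i5 stratification tool is run on medical records "to identify the most suitable cohort for this programme". One of its two target groups is those with "High Probability of currently having an undiagnosed LTC"; the other is those who may develop one soon.
- Section 3.1: entry turns on three or more long-term conditions, a medium to high frailty score, unsteadiness or falls, or atrial fibrillation, hypertension or heart failure.
- Section 4, opening text: "We will choose about a third of our participants from those who reside in a nursing care home and residential homes", and the reason given is "since they will tend to be sicker and more likely to have" an event. Section 3.4.1 gives a similar reason. Section 3.2.2 allows a smaller share, and there care-home staff select the residents.

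The performance measures named, in section 1.3 and again in section 5.2, are "sensitivity and specificity analyses to help determine the confidence of the predictive systems". Section 4 speaks of a sample that will "facilitate the eventual solution economically scaling up to meet the rapidly growing and aging population". No intended-use population is defined.

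**The concern.** The care-home share is chosen because its residents are expected to have more of the outcome that the models are to predict. Stage (a) nevertheless describes the resulting data as representative, and nothing in the protocol connects the two. Two consequences are possible.

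First, setting separates people with events from people without. If performance is summarised over both settings together, part of it can come from setting and not from any device. Setting need not be an explicit input: the LifeLight tablet is shared in care homes (section 3.4.1), and postcode or postcode sector is linked to each participant (sections 4.1 and 4.2). This bears on the principal question in section 2.1, whether device information predicts demand.

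Second, predicted risk and predictive value reflect the event rate of the cohort. Phase 2 derives qualitative and economic benefits from these data, so a benefit figure taken outside the cohort would carry that event rate with it.

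**Working it through.** There is no plan figure to reproduce: the protocol gives no event rate, accuracy target or sample-size derivation. Every rate below is an assumption chosen to show scale.

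**Inputs.** From the protocol: 500 participants (section 3.1) and a care-home share w of about 1/3 (section 4), so about 167 in care homes and 333 at home. Assumed: six-month event rates of 15% at home and 30%, 40% or 50% in care homes; sensitivity and specificity of 80%; a comparison population with 4% in care homes.

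**1. What setting alone achieves.** For a yes/no marker, AUC = 0.5 + [P(care home | event) − P(care home | no event)] / 2.

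| Care-home rate | Pooled event rate | P(care home given event) | P(care home given no event) | AUC |
|---|---|---|---|---|
| 30% | 20.0% | 0.500 | 0.292 | 0.604 |
| 40% | 23.3% | 0.571 | 0.261 | 0.655 |
| 50% | 26.7% | 0.625 | 0.227 | 0.699 |

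The 40% row also gives the accuracy of a rule that flags every care-home resident and uses no device: sensitivity 57%, specificity 1 − 0.261 = 74%. In a population with 4% in care homes, the same rule has sensitivity 0.016/0.160 = 10% and specificity 1 − 0.024/0.840 = 97%. Sensitivity and specificity can therefore move with case mix.

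**2. Pooled against within-setting discrimination.** A simulation (normally distributed score combined with the odds implied by setting, 400,000 draws, rates 40% and 15%) gave:

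- within-setting AUC 0.50 (useless signal): pooled 0.66
- within-setting AUC 0.64: pooled 0.72
- within-setting AUC 0.71: pooled 0.77

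**3. Predictive value when only the setting mix changes.** PPV = 0.8p / [0.8p + 0.2(1 − p)], with p = w × 0.40 + (1 − w) × 0.15.

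- Study, w = 1/3: p = 0.233, PPV = 0.187/(0.187 + 0.153) = 54.9%
- w = 4%: p = 0.160, PPV = 0.128/(0.128 + 0.168) = 43.2%
- w = 0: p = 0.150, PPV = 0.120/(0.120 + 0.170) = 41.4%

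With rates of 30% and 10%, the move from w = 1/3 to w = 4% takes PPV from 44.4% to 32.6%.

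**4. Sensitivity of this result.**

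- Care-home share of one sixth (40% and 15%): p = 0.192, PPV = 48.7%, so the fall to 43.2% is 5.5 points.
- If the algorithm had also doubled the own-home rate (7.5% outside the study): p = 0.04 × 0.40 + 0.96 × 0.075 = 0.088, PPV = 27.8%. The protocol gives no such factor.
- Equal rates of 20% in both settings and no enrichment by the algorithm: PPV stays at 50.0%, and pooled and within-setting AUC agree. The effect is nil.

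**The case against.** The strongest reply is that stage (a) belongs to a generic outline. It can be read as asking only for patients both with and without the event within the target group, and the sentence before the outline refers to targeted screening. That softens the conflict but does not remove it: the same word still describes a cohort selected on expected risk, and the target group is not named.

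Further replies stand and limit the point:

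- The protocol does not say that results will be pooled, and it never names predictive value. Stage (c) plans testing for quality and applicability. Reporting by setting could sit in an SAP that is not at hand, so its absence is not itself a fault.
- The algorithm selects mainly own-home participants. Care-home residents are picked by staff and are only very likely to be on the same lists (section 3.2.2).
- The scaling sentence in section 4 is about sample size and cost. It does not claim that accuracy transfers.
- Section 5.2 also plans a comparison with a similar cohort outside the study, so the benefit case does not rest on model accuracy alone.

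A reader might infer that performance will fail outside the cohort, with predictive value collapsing. At 80%/80% the formula does give 31%, 17% and 11% at event rates of 10%, 5% and 3%. All three rates lie below the 15% assumed for own-home participants, so a change in setting mix cannot produce them. They need a further fall in own-home risk, for which the protocol offers no figure.

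**Conclusion.** The point holds in a limited form. The description in stage (a) conflicts with selection on expected risk in sections 3.1, 3.4.1, 4 and 5.1.1, and nothing in the protocol reconciles them. Enrichment itself is not an error.

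The consequence is conditional: performance may not carry to a population with a different mix, and setting may look predictive if results are pooled. Under the assumed rates, setting alone is worth an AUC of 0.60 to 0.70, and the setting mix alone is worth about 12 to 14 points of PPV (55% to 41-43%). A smaller care-home share shrinks this, and equal rates with no enrichment by the algorithm remove it. The protocol itself expects care-home residents to have more events, which supports the direction but not any particular size. The documents do not support saying that results will not transfer, or that the benefit case is overstated by a known amount.

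**What to change.** In section 5.2, replace the claim of representativeness with a statement that the cohort is risk-enriched. Name the intended-use population and limit conclusions to it.

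Report discrimination and calibration separately for own-home and care-home participants. Report the contribution of device data as the gain over a model using records and setting only.

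If predictive value or economic benefit is projected beyond the cohort, show it over a stated range of event rates. Routine data for the eligible population would help where access allows, but this is not assured: section 5.2 filters extraction to participants, although section 4.2 is broader, and the data-access application in section 5.3 is still to be completed.

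The cost is wording and a few tables, with no new participants. The downside is less favourable headline figures and wider intervals within each setting, the care-home stratum included. At 40% and 15%, with 80% sensitivity and specificity and all 500 participants used (half-width = 1.96 × √(0.16/n)):

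- Sensitivity: ±9.6 points in care homes (67 events) and ±11.1 at home (50 events), against ±7.3 pooled (117 events).
- Specificity: ±7.8 points in care homes (100 non-events), against ±4.0 pooled (383 non-events).

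A held-out test set would widen all of these.

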3.1 Participant eligibility

The research team aim to recruit 500 participants to take part in the study. In order to achieve this target number, the research team aims to identify at least 700 potential participants according to the following inclusion and exclusion criteria.

Inclusion Criteria

- Individuals over the age of 18 that:
 - Have 3 or more long-term conditions AND/OR
 - Have a medium to high frailty score AND/OR
 - Are suffering from unsteadiness or falls AND/OR
- Those who are found to have paroxysmal and/or asymptomatic atrial fibrillation (AF), hypertension or heart failure
- Live in their own homes or in residential care homes or in nursing care homes

Exclusion criteria

- Children
- Individuals for whom consent cannot be obtained (i.e. individuals with severe mental impairments or learning difficulties)
- Patients on palliative care
- Individuals lacking mental health capacity or whose mental health conditions might be influenced by participating in the study?
- Individuals who's mental capacity deteriorates during the study period will be removed from the study.

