3.4 Participant onboarding

3.4.1 Allocation of devices

Once participants have provided their consent, each will receive a phone call from Optima Systems Ltd to:

- Ensure the information provided is correct
- Check that the participant is still happy to proceed
- Reiterate the key points of information provided in the Participant Information Sheet
- Establish the current technical capability of each participant i.e. WiFi connectivity

We intend to choose the most suitable smart technology for each patient. The choice of the smart technology is based on careful judgement and we will aim to develop an approximate "right app or wearable for the right patient" as clearly as we can. We will do this based on the initial conversation held with the participant.

Since patients do not necessarily become ill with the same conditions they already have, one or at most two devices per patient will be chosen. We are aiming to include about a third of the patients from residential and care homes since they will tend to be more vulnerable and more likely to have an adverse health event and certain apps can be used by smart devices can be installed from the internet.

The questionnaires will be sent and completed by the patient on the smart phone, tablet or desktop. We currently are considering how we can safely use the same tablet in a Care home to obtain clinical information on respiratory and heart rate and BP oxygen saturation on several patients. This will involve engaging with the residential and care home staff to develop safe procedures; this will be helped by the knowledge of the Covid-19 status of both patients and staff in terms of blood antibody tests on all the staff and all the patients. We hope also that the availability of PPE (Personal Protective Equipment) will be confirmed in each of the relevant homes.

The next action will be to arrange for the participants to receive the wearable or smart technology and to be shown how to use it by the "research supporter" with the aid of the internet. We will be allocating participants randomly according to their circumstances, to receive two (or at most three) wearables or smart technologies.

Commented [CP3]: Updated slightly as we have concluded device allocation will be random to an extent – please ensure my wording is accurate here

Commented [**CP4**]: I think we should go further here and propose a process otherwise it is quite a big question mark this will link back to the SOP you are developing [name].

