4.2 Pseudonymised data content

At the end of the pseudonymised data collection phase, we will have drawn from 4 main sources for each participant:

- a. Pseudonymised data drawn from wearables, sensors, devices and monitors
- b. Pseudonymised related data drawn from several NHS sources
- c. Geographically related data drawn from environmental sources (MetOffice, DEFRA)
- d. Pseudonymised participant (with multiple morbidities) related questionnaire results including participant outcome measures

Pseudonymised data drawn from wearables, sensors, devices and monitors – individual participant specific (anonymised) data which will include: See table B above.

a. Pseudonymised patient data drawn from NHS including:

- GP or HCP attendances (or visits) in the period of study and would include reason for attendance
- NHS Hospital Episode Statistics (HES) data for South Lincolnshire, containing details of all
 admissions, outpatient diagnoses and A & E attendances, together with GP data records
 for the whole patient group for the 2 years preceding the study together with the study
 period and one year into the future to evaluate impact.
- Known procedures (OPCS, SNOMED CT, etc.)
- Prescribed drugs and changes in the period of the study (and make this for 2 year preceding the study and one year into the future).
- GP Data and Social Prescribing Data.
- Post code or postcode sector of patients to facilitate linkage to the deprivation index (IMD) and environmental data.
- Death or other severe events

19

b. Data drawn from environmental sources will include:

- Air quality and weather pollutant levels e.g. temperature, dew point, etc.
- Postal sector of pseudonymised patients
- c. QuestLink questionnaires at intervals including:
 - HowRu and Health Confidence Score (HCS) Person Reported Measures of Outcomes
 - Questions about events in the family
 - Medication related questions including use of "over the counter medications"
 - Activity levels

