5.2 Data analysis

The use of Artificial Intelligence (AI) is being increasingly used as predictive healthcare solutions to provide early detection of long term conditions that anticipate and can thereby prevent illness and disease. One such common example of this technology used for screening is Atrial Fibrillation (AF) which utilises Artificial Intelligence techniques such as Principal Component Analysis (PCA) and Neural Networks (NN) (Ref Braun 2018). Artificial Neural Networks (ANNs) provide a powerful technique for modelling complex non-linear relationships for classification. Neural Networks are commonly applied in non-linear predictions to analyse the complex relationships and correlation that exist between patient history including the social determinants of health, and development of future conditions, and also between the physiological and behavioural measurements.

The NHS has the great advantage of having vast amounts of historic patient data in standardized form suitable for analysis and AI training. The Healthcare industry is data-rich, but it is not always possible to extract the required information from the data in a timely manner or in a manner that is useful to the patient or healthcare professional.

As a separate part of the study (phase 2) we intend to make assessments of the likely qualitative and economic benefits of the predictive system based on the data collected. These will be tested through data quality evaluation, model selection, training data categorisation, leaning algorithm(s), sensitivity and specificity analyses to help determine the confidence of the predictive systems (Ref: Longstaff 2010). The benefits can accrue in several parts of the "services". We will attempt to define the proportions in each.

Benefits will accrue to the patient, the family and work; they will also accrue to the health and social services when the specific event or illness is avoided. We will study trends across the cohort that were part of the PoC (patient participation groups PPG) compared with a similar cohort of patients that were not part of the PoC (patients reference group PRG) and report on the findings.

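### The three-way data split in Section 5.2 is not tied to the participant and, read as a hold-out on at most 500 people, would probably give an imprecise sensitivity; participant-level cross-validation would do better at little cost

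*Protocol*

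**What the plan says.** Section 5.2 of the protocol outlines five broad stages of model development. Stage a) calls for a cross-section of "patients with and without the condition or an adverse event". Stage c) is "Split the data for machine learning training, monitoring of overfitting and performance testing to facilitate evaluation of prediction quality and applicability". Stage d) then trains several models and topologies and picks the combination that performs best. No test share, unit of split or resampling scheme is given.

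The same section, in its account of phase 2, names "sensitivity and specificity analyses to help determine the confidence of the predictive systems"; Section 1.3 says much the same.

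On size, Section 3.1 states: "The research team aim to recruit 500 participants to take part in the study". The device table in Section 3.4.1 plans FibriCheck for 300 of them. On duration, Section 1.3 states: "For a period of approximately six months we will record their vital signs". On setting, Section 3.4.1 states: "We are aiming to include about a third of the patients from residential and care homes"; Section 3.2.2 allows for fewer.

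The outcome is left broad. Section 4.2 collects "GP or HCP attendances (or visits) in the period of study" as well as hospital records that continue "one year into the future to evaluate impact", and Table C runs from outpatient visits to heart attack. No expected number of events and no target precision for sensitivity appears.

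**The concern.** The hypothesis in Section 2.1 begins with whether device data can predict demand for services, and sensitivity and specificity are the measures named for judging the predictive system. Their quality depends on how the test data are formed.

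Two problems follow from the wording of stage c).

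- **Few events.** If people are held out, only a fraction of at most 500 is used for testing, and only those with an event inform sensitivity. The historic NHS records that Section 5.2 also mentions are not said to carry device data, so they cannot enlarge this test set.
- **Leakage.** Most devices give daily readings for about six months. Splitting those readings gives a large-looking test set, but the same person then appears in both training and test data, and a model can score by recognising the person. Residents of one care home, who may share a tablet, raise the same problem at home level. The wording of stage c) does not rule this out.

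The choice of a best combination in stage d) adds to the need for test data that are clean at the level of the person.

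**Working it through.** The protocol has no event count or precision figure to reproduce, so the check starts from its sample size and declared assumptions.

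**Inputs**
- N = 500 (Section 3.1), the recruitment target, with no dropout deducted.
- Test share f = 20%: assumed.
- Proportion with an event r = 10%, 20% or 40%: assumed.
- Sensitivity p = 0.70: assumed.

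**Step 1: people with an event in the test set, n = N × f × r**
- 500 × 0.20 × 0.10 = 10
- 500 × 0.20 × 0.20 = 20
- 500 × 0.20 × 0.40 = 40

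The other 60-90 of the 100 test participants inform specificity, so sensitivity is the weaker of the two.

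Range under other assumptions:
- 15% share and 5% with an event: 500 × 0.15 × 0.05 ≈ 4.
- One-third share and 60% with an event: 500 × 1/3 × 0.60 = 100.
- FibriCheck users only, 20% share: 300 × 0.20 × 0.10 = 6 up to 300 × 0.20 × 0.40 = 24.

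**Step 2: 95% Wilson interval**

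Limits = [p + z²/(2n) ± z√(p(1−p)/n + z²/(4n²))] / (1 + z²/n), with z = 1.96.

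For n = 10: centre = (0.70 + 0.192)/1.384 = 0.645; half-width = 1.96 × √(0.0210 + 0.0096)/1.384 = 0.248; interval 0.40-0.89.

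**Step 3: hold-out against testing every participant once out of fold (n = 500 × r)**

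| r | Hold-out events | Interval | Out-of-fold events | Interval | Width ratio |
|---|---|---|---|---|---|
| 10% | 10 | 0.40-0.89 | 50 | 0.56-0.81 | 0.247/0.495 = 0.50 |
| 20% | 20 | 0.48-0.85 | 100 | 0.60-0.78 | 0.177/0.374 = 0.47 |
| 40% | 40 | 0.55-0.82 | 200 | 0.63-0.76 | 0.126/0.273 = 0.46 |

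The out-of-fold intervals are binomial. True cross-validation intervals are somewhat wider, because the predictions are not fully independent.

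**Step 4: events needed for a half-width of 0.10 at p = 0.70**

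1.96² × 0.70 × 0.30 / 0.10² = 80.7, so 81 people with an event. A test set of 100 reaches this only if 81% have an event; all 500 reach it at 81/500 = 16.2%.

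**Step 5: splitting readings**

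The simulation had 500 people over 26 weeks, 12 person-specific features unrelated to risk, and a nearest-neighbour classifier. Across repeated runs the AUC was 0.63-0.65 when rows were split and 0.48-0.52 when people were split. The correct value is 0.50, so the row split shows apparent skill where there is none. The set-up is built to isolate the mechanism and does not predict the size of the bias in this study.

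**The case against.** The strongest reply is that stage c) names three uses of the data and no more. It sits in a list introduced as a broad outline. Nested cross-validation also divides data for those three uses, so it is compatible with the sentence. Fractions, unit of split and resampling scheme are commonly left to an analysis plan, which is not at hand. This stands: a reader might infer that the protocol commits to one random cut of the 500, but neither a single cut nor randomness is stated. The hold-out is the ordinary reading, not the only one.

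Other tempting readings go too far:

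- *That 10-40 events is a consequence of the protocol.* It is a product of two assumptions. If the outcome were any GP attendance, or if the extra year of records counted, there could be many more events; a rare outcome or separate models by event type would give fewer.
- *That sensitivity could not be usefully estimated.* At 40 events, 0.55-0.82 is wide but informative for a proof of concept, and the protocol sets no target to miss.
- *That splitting readings is the only way to a larger test set.* Held-out people can be scored over many time windows, or the split can run forward in time, which would suit the individual calibration period in Section 5.1.3. Windows from one person are correlated, however, and a forward split tests the same people later, not new ones.
- *That accuracy is the sole main result.* Section 5.2 mentions sensitivity and specificity under phase 2, and Section 2.1 also tests acceptability, ease of use and comfort.

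What remains is that the natural reading of stage c) uses a small cohort inefficiently, and that its wording allows a split that would inflate accuracy.

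**Conclusion.** The point holds as an inexpensive improvement, not as a fault that undermines the study. With a 20% test share and 10-40% of participants having an event, a participant-level hold-out tests about 10-40 people with an event. The 95% interval for a sensitivity of 0.70 then has a width of about 0.27 to 0.50. Using all 500 out of fold brings this to about 0.13 to 0.25, slightly more once dependence between predictions is allowed for. Dropout, or analysis of FibriCheck users alone, would lower the counts; a commoner outcome would raise them. The leakage risk is conditional: it arises only if readings rather than people are split, which the protocol neither states nor excludes.

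**What to change.** Reword stages c) and d) of Section 5.2 so that:

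- performance is estimated by repeated nested cross-validation over all participants with device data;
- the participant is the fold unit, and all residents of one care home stay in the same fold;
- tuning and the choice of the best-performing combination take place in the inner loop only;
- out-of-fold sensitivity and specificity are reported, with intervals from a bootstrap that resamples participants and homes.

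If the sponsor prefers a hold-out, it should state that the split is by participant and justify it with the expected number of people with an event in the test set and the resulting precision.

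The cost is the rewording of two bullets and more computing time. No further participants or data are needed. The reported accuracy may be less favourable than a leaky split would show.
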